5.8. Treatment Failure

For each part below, subjects who meet any of the following criteria will be considered as a treatment failure and considered as a non-responder in the efficacy analysis:

Part A

- Subjects who initiate or increase SLE standard of care therapy or other disallowed concomitant therapy (Table 8 of the latest protocol version) during the treatment period of the study.
- Subjects with corticosteroid dose increase above baseline during the treatment period except for what is allowed under rescue 1 during week 1 to 4.
- Subjects with more than 2 allowed rescues between week 1 to week 12.
- Subjects with any increase in corticosteroid during treatment period after week 20.

CONFIDENTIAL

The information contained herein may not be used, disclosed, or published without the written consent of Biogen MA Inc.

Part B

- Subjects who initiate disallowed concomitant therapy during treatment period of Part B (see Table 8 of the latest protocol version).
- Subjects who initiate or increase SLE/CLE standard of care therapy during the treatment period of the study.
- Subjects who initiate or increase corticosteroid dose above baseline during the treatment period of the study (oral or topical except those in Table 6 of the latest protocol version).

Note: Treatment failure subjects would be allowed to remain in the trial and receive investigational product, as applicable)

More detailed definition regarding specific concomitant therapy is described in and addendum to this SAP. For both parts, subjects' data considered as treatment failure will be handled as described in [Section 6.6](#).

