11.4.1.1.1. Background Therapies for Lupus

11.4.1.1.1.1. Systemic Lupus Erythematosus

Standard of care therapy that may be continued during the study for SLE includes 1 of the following single immunosuppressants or immunomodulators, delivered via IV, SC, or oral administration: azathioprine (up to 200 mg/day), 6-mercaptopurine (up to 100 mg/day), mycophenolate (either as MMF at up to 3 g/day or MPS up to 2160 mg/day), and methotrexate (up to 25 mg/week). Other permitted SoC therapies include antimalarial medications such as hydroxychloroquine (up to 400 mg/day), quinacrine (100 mg/day), chloroquine (up to 250 mg/day), and dapsone (up to 150 mg/day) as well as corticosteroids (see Section 11.4.1.1.2) and NSAIDs (see Section 11.4.1.1.3.1).

All background therapy for SLE given prior to Screening or randomization must have been kept stable or discontinued as specified in the inclusion/exclusion criteria for a subject to be eligible for the study. These medications must remain stable during Screening or randomization as well as the 24-week (Part A) or 16-week (Part B) Treatment Period, with the exception of the 2 corticosteroid rescue attempts allowed during corticosteroid tapering in Part A of the study (Section 11.4.1.1.2). No initiation of new immunosuppressant therapy or increase in dose of current immunosuppressant is allowed. Subjects who initiate SLE SoC therapy during the study will be considered treatment failures. They are encouraged to continue receiving study treatment and complete the study at the Investigator's discretion.

Standard of care medications that are part of the subject's previous SLE treatment will not be provided by Biogen.

CONFIDENTIAL

The information contained herein may not be used, disclosed, or published without the written consent of Biogen MA Inc.

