returned to the last oral corticosteroid dosage prior to rescue level within 7 days. A dose increase is not permitted within 1 week of a planned study visit.

Week 8:

Decrease as per tapering schedule. No increases are allowed.

Week 9 to Week 11:

Decrease as per tapering schedule. One oral corticosteroid rescue (Rescue 3) for SLE activity is allowed up to a dose no higher than the previous dosage level, but the dose must be returned to last oral corticosteroid dosage prior to rescue level within 7 days. A dose increase is not permitted within 1 week of a planned study visit.

Week 12:

No increase or decrease allowed.

Week 13 to Week 16:

Stable dosage or decrease as per the tapering schedule (no increase is allowed). The corticosteroid dose must always be \leq Week 12 dose.

Week 17 to Week 24:

Stable dosage at Week 16 dosage, no increases or decreases are allowed.

CONFIDENTIAL

The information contained herein may not be used, disclosed, or published without the written consent of
Biogen MA Inc.

Table 7: Oral Corticosteroid Tapering Schedule

Allowable OCS Rescue Dosing ¹	Timing by Weeks (Days)	OCS Starting Dose Prior to Tapering (mg/day)							
		20 mg	17.5 mg	15 mg	12.5 mg	10 mg	7.5 mg	5 mg	2.5 to <5 mg
Rescue 1	Week 1-4 ² (Day 1 to 28)	Stable 1 OCS rescue for SLE activity allowed up to maximum 10 mg/day above Day 1 dosage, but must return to Day 1 level within 7 days							
Rescue 2	Week 5 ³ (Day 29 to 35)	17.5	15	12.5	10	7.5	5	5 or 2.5	2.5 to <5
	Week 6 ³ (Day 36 to 43)	17.5	15	12.5	10	7.5	5	5 or 2.5	2.5 to <5
	Week 7 ³ (Day 44 to 50)	15	12.5	12.5	10	7.5	5	5 or 2.5	2.5
	Week 8 (Days 51 to 57)	15	12.5	10	7.5	7.5	5	5 or 2.5	2.5
Rescue 3	Week 9 ³ (Days 58 to 64)	12.5	10	10	7.5	5	2.5	2.5	0 to 2.5
	Week 10 ³ (Days 65 to 71)	12.5	10	10	7.5	5	2.5	2.5	0 to 2.5
	Week 11 ³ (Days 72 to 78)	10	7.5	7.5	5	2.5 to <5	2.5	2.5	0 to 2.5
	Week 12 (Days 79 to 85)	10	7.5	7.5	5	2.5 to <5	2.5	2.5	0 to 2.5
	Week 13-16 (Days 86 to 113)	Stable at Week 12 dose or decrease							
	Week 17-24 (Days 114 to 169)	Stable at Week 16 dose							

Abbreviations: OCS = oral corticosteroids; SLE = systemic lupus erythematosus.

¹ Two rescues are allowed out of the three described.

CONFIDENTIAL

The information contained herein may not be used, disclosed, or published without the written consent of Biogen MA Inc.

² Between Weeks 1 and 4 (Rescue 1). Once a dose is reduced it must not be re-increased, with the exception of the 1 time rescue.

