The reduction from baseline to Week 12 and 16 in the CLASI-A score will be calculated for each subject. The proportion of subjects who had ≥ 7 -point CLASI-A response at week 12 or week 16, defined as a ≥ 7 -point reduction in the CLASI-A score from baseline at week 12 or 16, will be analyzed separately for each time point as described for binary endpoint in [Section 6.1.2](#).

CONFIDENTIAL

The information contained herein may not be used, disclosed, or published without the written consent of Biogen MA Inc.

 Biogen	Statistical Analysis Plan 230LE201	<V 2.0>
--	---	----------------------

6.3.4. Percent Change in CLASI-A Score from Baseline at Week 12, 16 and 24 (Part A) and Week 12 (Part B)

The change from baseline to each post-baseline week in the CLASI-A score will be analyzed will be analyzed as described for continuous endpoint analysis in [Section 6.1.1](#) (Part A) and [Section 6.1.2](#) (Part B). Summary statistics for actual values and change from baseline will also be presented by week based on observed data.

6.3.5. Proportion of Subjects with an SLE Responder Index (SRI) Response of ≥ 4 at Week 24 (Part A Only)

SLE Responder Index (SRI) of ≥ 4 (SRI-4) at Week 24 is a categorical response variable (yes/no) incorporating the following criteria for achievement of responder status (i.e., all criteria must be met to achieve responder status):

- A reduction from baseline of ≥ 4 points in Systemic Lupus Erythematosus Disease Activity Index 2000 (SLEDAI-2K), and
- No new organ system affected, as defined by no new British Isles Lupus Activity Group (BILAG)-2004 grade A and no more than one new BILAG-2004 grade B, and
- No worsening from baseline in subject's lupus disease activity defined by <1 point increase in the Physician's Global Assessment (PGA) [visual analog scale (VAS)] (in the scale of 0-10) and
- No changes to protocol specified medications rules as described below (all criteria must be met):
 - No initiation or increase of SLE standard of care therapy or other disallowed concomitant therapy (see table 8 from latest protocol for protocol-prohibited list).
 - Concomitant corticosteroid dosage at Week 24 to be ≤ 10 mg/day.
 - Concomitant corticosteroid dosage at Week 24 to be \leq Day 1.
 - No increase in corticosteroid dose between weeks 17 and 24.

CONFIDENTIAL

The information contained herein may not be used, disclosed, or published without the written consent of Biogen MA Inc.

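### SAP 5.8 does not count as treatment failure a Part A steroid increase in Weeks 13–20 that stays at or below the baseline dose, so the later joint counts enter the primary analysis as observed

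*SAP*

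**What the plan says.** SAP 5.8 lists four routes to treatment failure in Part A:

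1. "Subjects who initiate or increase SLE standard of care therapy or other disallowed concomitant therapy", over the treatment period.
2. "Subjects with corticosteroid dose increase above baseline during the treatment period except for what is allowed under rescue 1 during week 1 to 4".
3. "Subjects with more than 2 allowed rescues between week 1 to week 12".
4. "Subjects with any increase in corticosteroid during treatment period after week 20".

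Under SAP 6.6.1, a failure's later joint counts are set aside and replaced by the poorer of the baseline value and the last value before failure. Under SAP 6.6.2, failures are non-responders on binary endpoints. A subject who is not a failure and remains on treatment contributes observed counts.

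Protocol 11.4.1.1.2.2 gives the dosing rules. For Weeks 13–16: "Stable dosage or decrease as per the tapering schedule (no increase is allowed". For Weeks 17–24: "Stable dosage at Week 16 dosage, no increases or decreases are allowed".

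The SRI-4 definition in SAP 6.3.5 includes "No increase in corticosteroid dose between weeks 17 and 24". It also caps the Week 24 dose at 10 mg/day and at the Day 1 dose.

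Protocol 16.1.2.1 makes a subject a definite failure for a rise above baseline after Week 4, apart from permitted use. Its stated reason is that steroid and rescue use affect the joint count. Other departures from the taper may be failures, depending on severity and timing, with details left to the SAP.

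**The concern.** The taper is mandatory and opens a gap between the baseline dose and the Week 12 dose. From Week 13 to Week 20 a subject can climb back into that gap, against the dosing rules, without meeting any steroid trigger in SAP 5.8. If the higher dose is kept to Week 24, the primary-endpoint joint count is taken on re-escalated steroid and treated as response to randomized treatment. That is the contamination Protocol 16.1.2.1 gives as its reason for removing joint counts after steroid increases.

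The same event is then handled differently by endpoint and by week. From Week 17 it fails SRI-4 but leaves the primary endpoint untouched. A smaller rise at Week 21 counts against both. No reason is given for starting the any-increase trigger at Week 20.

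**Working it through.** **Planned figures.** Protocol 16.8 assumes 50 per arm, 20% dropout (40 per arm), SD 6, a difference of 2.5 and two-sided alpha 0.2. The standard error is 6 × √(2/40) = 1.342, and 2.5/1.342 = 1.863. Power is Φ(1.863 − 1.282) ≈ 0.72 (0.717 with the t distribution), against the stated 71%. With 170 subjects (68 per arm) it is 0.874, against 87%. Both reproduce, and nothing in this point changes them. SAP 11 prints alpha 0.02, which gives about 0.32; that is a separate discrepancy.

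**The rules side by side, using the protocol's day numbering.**

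| Period | Protocol dosing rule | SRI-4 rule on increases | SAP 5.8, rise above baseline | SAP 5.8, rise at or below baseline |
|---|---|---|---|---|
| Weeks 13–16 (Days 86–113) | none allowed | none stated | failure | not named |
| Weeks 17–20 (Days 114–141) | none allowed | non-responder | failure | not named |
| Weeks 21–24 (Days 142–169) | none allowed | non-responder | failure | failure |

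The uncovered window is 141 − 86 + 1 = 56 days. Of these, 141 − 114 + 1 = 28 lie inside the SRI-4 no-increase period.

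**Room for it to happen.** Protocol Table 7, baseline dose minus Week 12 dose: 20 − 10 = 10 mg; 17.5 − 7.5 = 10; 15 − 7.5 = 7.5; 12.5 − 5 = 7.5; 10 minus (2.5 to <5) = more than 5, up to 7.5; 7.5 − 2.5 = 5; 5 − 2.5 = 2.5. A subject on no steroid at baseline has no such room, since any start is above baseline.

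**Two subjects, both tapered from 20 to 10 mg by Week 12.**
- Subject 1 goes to 17.5 mg at Week 18 and stays there. The dose is below baseline, is not a Week 1–12 rescue, and did not rise after Week 20. No steroid trigger is met, and the Week 24 count is used as observed. For SRI-4 the subject fails on the increase and on the 10 mg cap.
- Subject 2 goes to 12.5 mg at Week 21. The fourth trigger applies, and Week 24 is imputed as failure.

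**Size, by illustration only.** Let rP and rA be the fractions of each whole arm that re-escalate in the window. Let s be the imputed failure change minus the observed change, in joints. To a first approximation (arm means, ignoring covariates), the placebo-minus-active difference as written is smaller than under an aligned rule by

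shift = (rP − rA) × s.

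Two sets of assumed s are shown: 4 and 8; and 6.5 and 9.5, from an imputed change of +0.5 against observed changes of −6 and −9.

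| rP / rA | s = 4 | s = 6.5 | s = 8 | s = 9.5 |
|---|---|---|---|---|
| 5% / 5% | 0 | 0 | 0 | 0 |
| 5% / 2% | 0.12 | 0.20 | 0.24 | 0.29 |
| 10% / 5% | 0.20 | 0.33 | 0.40 | 0.48 |
| 20% / 10% | 0.40 | 0.65 | 0.80 | 0.95 |

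Check of the last cell, with assumed changes of −6 (placebo) and −8.5 (active) in other subjects:
- As written: placebo 0.8 × (−6) + 0.2 × (−9) = −6.6; active 0.9 × (−8.5) + 0.1 × (−9) = −8.55; difference 1.95.
- Aligned: placebo 0.8 × (−6) + 0.2 × 0.5 = −4.7; active 0.9 × (−8.5) + 0.1 × 0.5 = −7.6; difference 2.90.
- Shift: 2.90 − 1.95 = 0.95.

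If rA exceeds rP, the sign reverses.

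**Do other planned analyses test this?** The reference-based imputation in SAP 6.6.1 uses the same SAP 5.8 definition, so it does not. The retrieved-dropout analysis in SAP 6.10 keeps all post-failure data, so it does not either. The per-protocol analysis might, depending on an addendum that is not among these documents.

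**The case against.** **The gap is narrow, and the protocol leaves it to the SAP.** A reader might infer that SAP 5.8 ignores every steroid increase before Week 20. It does not: the above-baseline trigger runs through the whole treatment period and the rescue count covers Weeks 1–12. A reader might also infer that SAP 5.8 contradicts the protocol's failure definition. It does not plainly do so, because the protocol's definite trigger is itself relative to baseline and its wording on other increases is permissive. Both corrections stand. But a task delegated to the SAP still has to be done there, and SAP 5.8 is silent on this case.

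**SRI-4 may be stricter by design.** A composite can carry its own steroid rule, and this one covers only Weeks 17–24, so Weeks 13–16 rest on the dosing rule alone. That stands. It does not explain why the any-increase trigger for the primary endpoint begins at Week 20.

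**The standard-of-care trigger may already catch it.** Protocol 11.4.1.1.1 lists corticosteroids among permitted standard-of-care therapies, and SAP 5.8 refers finer definitions to the addendum. The ambiguity is real. But reading the first trigger to cover every steroid increase would make the three steroid triggers redundant and would fail subjects who use the rescues the third one tolerates.

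**The aligned rule overshoots.** In the illustration it gives 2.9 when the difference among other subjects is 2.5. That is how the plan chose to score failures: a failure's imputed change cannot be an improvement. Once failures occur, 2.5 is no longer the quantity this analysis targets, so the overshoot is no argument for classifying like cases differently.

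**Conclusion.** The gap is real on the face of SAP 5.8 and affects the Part A primary analysis. It is confined to re-escalation from a tapered dose, in Weeks 13–20, to a level at or below baseline. It should be corrected, but it does not undermine the design.

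The effect is not established. Under the assumed rates it runs from 0 to about 0.8 joints with s up to 8, and to 0.95 with s = 9.5, against the planned 2.5. The rates are fractions of a whole arm, although only subjects who entered on steroids and tapered can contribute, so the upper rows are demanding. A reader might infer that the rule biases the trial against the drug. That needs placebo subjects to re-escalate more often. This is plausible if the drug works, but the documents do not state it. With equal rates the shift is zero, and with more re-escalation on active the rule as written favours the drug.

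The conclusion also assumes that the addendum does not already classify these increases.

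**What to change.** In the fourth Part A bullet of SAP 5.8, start the any-increase window no later than Week 17, so that it matches SRI-4, or directly after the Week 12 taper, so that it matches the protocol's no-increase period. If Week 20 was intended, give the reason. State whether the standard-of-care trigger covers corticosteroids, and define the dose against which an increase is judged.

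Reconcile SAP 5.8, SAP 6.3.5, Protocol 11.4.1.1.2.2 and Protocol 16.1.2.1. Protocol 11.4.1.1.2.2 also needs to agree with itself: its summary list ties the Weeks 17–24 dose to Week 12, while its week-by-week text and Table 7 tie it to Week 16.

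Do this before the IA2 database lock and unblinding, because SAP Appendix B schedules the model-based Part A primary analysis there.

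The cost is one line of SAP wording plus the cross-checks. Daily steroid use is already recorded in subject diaries. The downside is that a few more subjects will be scored as failures. Only the analysis classification changes; steroid management does not.

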6. EFFICACY ANALYSES

6.1. General Considerations

For both Part A and Part B, the efficacy analyses will be performed using the MITT population and will be considered as the primary analyses. For each endpoint, additional conditions may apply for pooling of data across protocol versions (see [Section 3.1](#)). The final model for each analysis in the MITT population will also be used for the PP analysis. A complete list of all the planned analyses and target population for the primary and secondary endpoints is provided in [Appendix A1](#) (Part A) and [Appendix A2](#) (Part B).

Unless otherwise specified, statistical testing across all efficacy endpoint will be performed to compare each BIIB059 dose (Part A: 450 mg; Part B: 50, 150 or 450 mg) with placebo at the 2-sided, 0.05 significance level. P-values and corresponding 95% confidence intervals (CI) will be provided. P-values will be rounded to three decimal points before assessing statistical significance.

CONFIDENTIAL

The information contained herein may not be used, disclosed, or published without the written consent of Biogen MA Inc.

 Biogen	Statistical Analysis Plan 230LE201	<V 2.0>
--	---	----------------------

Summary statistics will be presented for all endpoints at all visits including follow-up visits. For continuous variables, the summary statistics will include number of subjects with data, mean, standard deviation (SD), median, first quartile (Q1), third quartile (Q3), minimum and maximum. For categorical endpoints, the summary statistics will generally include: number of subjects in the corresponding analysis population, number and percentage of subjects in each category.

Unless otherwise specified, week 2, 4, 8, 12, 16, 20 and, 24 will be included in all Part A “by visit” MMRM analyses.

Unless otherwise specified, week 2, 4, 8, 12 and, 16 will included in all Part B “by visit” MMRM analyses.

Additional study part specific efficacy analyses considerations are described in [Section 6.1.1](#) (Part A) and [Section 6.1.2](#) (Part B)

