16.8. Sample Size Considerations

Part A:

The sample size for Part A is 100 subjects, randomized in a 1:1 ratio, with 50 subjects allocated to each treatment group. This sample size will provide approximately 71% power to detect a statistically significant difference in the Week 24 absolute change from baseline active joint count, assuming a standard deviation of 6, a maximal difference of BIIB059 over placebo of 2.5, a 20% dropout rate, and a 2-sided testing at the 0.2 level significance. Additional information will be provided in the Statistical Analysis Plan (SAP). If the study is not stopped for futility at the IA (details in Section 16.7), then up to 70 additional subjects may be added to Part A. If an additional 70 subjects are added, the power will increase to approximately 87% at Week 24.

Part B:

The planned sample size for Part B is 100 subjects, randomized in a 1:1:1:1 ratio, with 25 subjects per dosage arm of BIIB059 (50 mg, 150 mg, and 450 mg) and placebo. This sample size will provide approximately 90% power to detect a dose-response relationship in the Week 16 percent change from baseline score in CLASI-A score, assuming a standard deviation of 30, a maximal difference of BIIB059 over placebo of 27.5%, and a 20% dropout rate. Five different dose-response relationships will be tested at the 2-sided 10% significance level with the MCP-Mod method being used to control for multiplicity [Bretz 2005].

CONFIDENTIAL

The information contained herein may not be used, disclosed, or published without the written consent of
Biogen MA Inc.

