6.5. Multiplicity Adjustment

Part A

There will be no adjustment for multiplicity at interim or final analysis for the primary or secondary endpoints in Part A.

Part B

Multiple Comparison Procedure-Modeling (MCP-Mod) methodology ([Bretz et al. 2005](#)) will be used to test the dose-response relationship across 3 doses of BIIB059 and PBO for the percent change from baseline in CLASI-A score at interim and final analysis. Five dose-response trends will be tested using the optimal contrasts as determined by the MCP-Mod methodology such that the overall Type I error rate is controlled at 0.05 (one-sided testing).

There will be no adjustment for multiplicity with secondary efficacy endpoints at interim or final analysis.

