11. SAMPLE SIZE JUSTIFICATION

Part A:

The sample size for Part A is 100 subjects, randomized in a 1:1 ratio, with 50 subjects allocated to each treatment group. This sample size will provide approximately 71% power to detect a statistically significant difference in the Week 24 absolute change from baseline active joint count, assuming a standard deviation of 6, a maximal difference of BIIB059 over placebo of 2.5, a 20% dropout rate, and a 2-sided testing at the 0.02 level significance. If the study is not stopped for futility at the IA, then up to an additional 70 subjects may be enrolled into Part A. These may increase the power to approximately 87% at Week 24.

Part B:

The planned sample size for Part B is 100 subjects, randomized in a 1:1:1:1 ratio, with 25 subjects per dosage arm of BIIB059 (50 mg, 150 mg, and 450 mg) and placebo. This sample size will provide approximately 90% power to detect a dose-response relationship in the Week 16 percent change from baseline score in CLASI-A score, assuming a standard deviation of 30, a maximal difference of BIIB059 over placebo of 27.5%, and a 20% dropout rate. Five different

CONFIDENTIAL

The information contained herein may not be used, disclosed, or published without the written consent of Biogen MA Inc.

dose-response relationships will be tested at the 2-sided 10% significance level with the MCP-Mod method being used to control for multiplicity. Further details about the dose-response analyses can be found in [Section 6.2](#).

The power calculations are based on assuming a standard deviation of 30, a maximal difference of BIIB059 over placebo of 27.5% at 450 mg, and a 20% dropout rate.

CONFIDENTIAL

The information contained herein may not be used, disclosed, or published without the written consent of Biogen MA Inc.

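### SAP 6.1 rounds p-values to three decimals before judging significance, so dose-versus-placebo tests run at 0.0495 or 0.0505 rather than 0.05 and can disagree with their own 95% CIs; the effect is very small

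*SAP*

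**What the plan says.** SAP 6.1 (General Considerations) makes three statements in one paragraph about efficacy testing. Each BIIB059 dose is compared "with placebo at the 2-sided, 0.05 significance level". Then "P-values and corresponding 95% confidence intervals (CI) will be provided". Then "P-values will be rounded to three decimal points before assessing statistical significance".

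The SAP does not say whether significance means p < 0.05 or p <= 0.05, and it does not adjust the intervals to match a shifted cut-off. Neither document limits the rounding to display.

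SAP 6.1.1 and 6.1.2 apply these comparisons through MMRM for continuous endpoints and logistic regression for binary endpoints, with a 95% CI for each odds ratio. On multiplicity, SAP 6.5 says of Part A: "There will be no adjustment for multiplicity at interim or final analysis for the primary or secondary endpoints in Part A". In Part B it leaves the secondary endpoints unadjusted. The Part B dose-response test (MCP-Mod) has its level set separately, at one-sided 0.05 in SAP 6.5 and at the equivalent 2-sided 10% in SAP 11.

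**The concern.** Rounding a p-value for a table is harmless. Rounding it before the decision moves the cut-off. The rule also puts a lump of probability exactly on 0.050. For an unrounded continuous p-value, the choice between < and <= has no practical effect. After rounding, that choice settles every result in a band 0.001 wide, and the SAP leaves it open.

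Two things are at stake. The stated error rate is not exactly the one used. And a result can be called significant beside a 95% CI that includes no effect, or not significant beside one that excludes it. The second would be awkward in a study report, because the SAP promises test and interval as a pair.

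**Working it through.** **Inputs.** Level 0.05, 2-sided, with 95% CI and rounding to three decimals (SAP 6.1). For a numerical example, the Part A planning figures: 50 per arm (Protocol 16.8, SAP 11), "assuming a standard deviation of 6, a maximal difference of BIIB059 over placebo of 2.5, a 20% dropout rate" (Protocol 16.8), so 40 per arm remain.

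**Step 1: the stated level.** With an exact test and no true effect, p is uniform on (0, 1). Judged unrounded, P(p < 0.05) = 0.0500, which is the plan's figure.

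**Step 2: the level after rounding.**
- If significance means p < 0.05, the rounded value must be 0.049 or less, so raw p < 0.0495. Level 0.0495.
- If significance means p <= 0.05, the rounded value may be 0.050, so raw p < 0.0505. Level 0.0505.

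A simulation of 20 million uniform p-values gave rejection rates of 0.05007 unrounded, 0.04958 under < and 0.05057 under <=. The rounded and unrounded decisions differed in 0.00050 of draws under each convention.

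**Step 3: conflict with the interval.** SE = 6 × √(2/40) = 1.342, with 78 df and critical t = 1.991 at 0.05. The difference is written as positive in favour of BIIB059.

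| Raw p | Prints as | Estimate | 95% CI | Call |
|---|---|---|---|---|
| 0.0504 | 0.050 | 2.666 | −0.005 to 5.337 | Significant under <=, yet the CI includes 0 |
| 0.0496 | 0.050 | 2.676 | 0.005 to 5.347 | Not significant under <, yet the CI excludes 0 |

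So conflict arises for raw p from 0.0495 to 0.0500 under <, and from 0.0500 to 0.0505 under <=. One convention must apply, so one of the two half-bands is always live, and never both.

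**Step 4: size over many tests.** Named primary and secondary comparisons with placebo:
- Part A: joint count 1; percent change in CLASI-A 3; CLASI-50, 4-point and 7-point responses 3; SRI-4, SLEDAI-2K, BILAG and PGA 4. Total 11.
- Part B (three doses): primary 3; percent change at Week 12, 3; three responder endpoints × two visits × three doses, 18. Total 24.

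That is 35, or roughly 30. With no true effects, the chance that any decision changes is at most 30 × 0.0005 = 1.5% (independent tests: 1 − 0.9995^30 = 1.5%). For all 35 it is at most 35 × 0.0005 = 1.75%. The Part B tests share a placebo arm and many are cut-points of one score, so there are effectively fewer tests.

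**Step 5: effect on power.** Part A, 40 per arm, normal approximation:

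| Level | Critical t (78 df) | Power |
|---|---|---|
| 0.0495 | 1.995 | 46.0% |
| 0.0500 | 1.991 | 46.2% |
| 0.0505 | 1.986 | 46.3% |

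Unrounded to one decimal, the powers are 0.4598, 0.4615 and 0.4632. At the planned effect the chance of a changed call on one test is therefore about 0.0017, some three times the null value. The 1.5% is a null figure and does not bound that case.

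**The case against.** The strongest reply is that this is immaterial. The rule is prespecified and mechanical, the study is Phase 2, and no gatekeeping step among these comparisons hangs on a borderline p-value. That stands as an argument about weight. It does not make the rule consistent with the stated level or with the promised intervals.

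A reader might infer that the rule inflates type I error. The documents do not support that. The direction is undetermined, and under the common convention p < 0.05 the rule is conservative.

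A reader might also size the problem on the whole 0.001-wide band, giving about 3% over 30 tests (1 − 0.999^30). That is the chance that some p-value prints as 0.050. A decision changes in only half the band, so the right figure is half as large.

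A third inference is that the rule governs the Part B dose-response test. SAP 6.1 does not exempt it expressly, but the paragraph concerns dose-versus-placebo comparisons at 2-sided 0.05 and gives way to anything set elsewhere. MCP-Mod has its own level and no CI is specified for its contrasts, so the interval conflict cannot arise there. If the rule did apply, the simulated critical value (five SAP candidate shapes, 20 per arm, 76 df) would move only from 1.979 to 1.984 or 1.975.

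Finally, rounding first has one merit: the verdict can be read from the printed value. Judged unrounded, 0.0497 and 0.0503 both print as 0.050 with opposite verdicts. A fourth printed digit for such values removes the difficulty.

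It is also fair to say that the Part A level has a larger, separate conflict: the Protocol powers Part A for "2-sided testing at the 0.2 level significance", the SAP for "2-sided testing at the 0.02 level significance", and SAP 6.1 tests at 0.05.

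**Conclusion.** The point holds as a minor inconsistency. The dose-versus-placebo comparisons do not run exactly at the stated 2-sided 0.05. The level is 0.0495 or 0.0505, depending on an inequality the SAP does not state, and in either case a decision can contradict its matching 95% CI. The shift is 0.0005 per test and at most about 1.5% over 30 null comparisons. The conflict with the interval is confined to the MMRM and logistic comparisons.

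This rests on two assumptions: that p-values are uniform under the null (approximate for MMRM with Kenward-Roger degrees of freedom and for logistic models), and that each interval comes from the same statistic as its p-value. It is a tidying change and does not threaten the trial's conclusions.

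**What to change.** Replace the rounding sentence in SAP 6.1 with:

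> Significance is assessed on unrounded p-values (p < 0.05 unless another level is specified); p-values are displayed to three decimals, with a fourth digit shown when the value would print as 0.050.

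This restores the stated level, makes each decision agree with its matching 95% CI, and settles the inequality before unblinding. The cost is one edited sentence and a trivial change to the table display format. No analysis, sample size or data collection changes.
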